- Occurrence of AEs, resulting in discontinuation of trial drug that is desired or considered necessary by the investigator and/or the subject (if applicable).
- Occurrence of pregnancy (if applicable).
- Use of a non-permitted concomitant drug, as defined in [Section 5.5.2](#), in which the predefined consequence is withdrawal from study drug (Sponsor may be contacted to discuss whether trial treatment must be discontinued).
- Noncompliance for non-medical reasons ([Section 6.4.1.11](#))

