### **5.5.2. Prohibited and/or Restricted Treatments**

As stated in the exclusion criteria ([Section 4.3](#)), subjects must not have had chemotherapy, radiotherapy (other than palliative bone-directed radiotherapy, as described in [Section 5.5.1](#)), major surgery, or received another investigational agent within 28 days before the start of study treatment.

Subjects are prohibited from receiving the following therapies and treatments during the Screening and Treatment periods of this trial:

- Immunotherapy not specified in this protocol.
- Chemotherapy.
- Investigational agents other than AGEN2034.
- Surgery for symptom management or tumor control.
- Growth factors (granulocyte colony-stimulating factor or granulocyte macrophage colony- stimulating factor). Exception: Erythropoietin and darbepoietin alpha may be prescribed at the investigator's discretion. Therapeutic use of G-CSF is allowed in subjects with Grade 3 or 4 febrile neutropenia.
- Radiation therapy for tumor control.
- Glucocorticoids for any purpose other than to modulate symptoms from an irAE, or for use as a pre-medication in subjects with a known history of an IV contrast allergy administered as part of computed tomography (CT) radiography.

Note: Replacement doses of corticosteroids (for example, prednisone 5-7.5 mg daily) are permitted while on study.

Note: Use of inhaled or topical corticosteroid is permitted.

- Bisphosphonates and/or receptor activator of nuclear factor kappa-B ligand (RANKL) inhibitor therapies cannot be initiated after informed consent has been signed. These therapies may be continued IF treatment with an agent from one of these two classes was initiated PRIOR to signing informed consent.
- Subjects who, in the assessment by the investigator, require the use of any of the aforementioned treatments for clinical management should be removed from the trial.
- Subjects may receive other medications that the investigator deems to be medically necessary.
- Medications listed in the Exclusion Criteria are prohibited in this trial.
- There are no prohibited therapies during the Post-Treatment Follow-up Phase

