Full serum chemistry 	X								X	X	X			
Hematology tests 	X		X	X			X	X	X	X	X			
Coagulation tests 	X			X			X		X	X	X			
Endocrine function tests 	X			X			X		X	X	X			
Urinalysis 	X			X			X		X	X	X			
Serum pregnancy test	X 													
Urine pregnancy test		X 					X		X	X	X			
Study drug administration 														
AGEN2034			X		X		X	X						

Abbreviations: ADA: anti-drug antibody; AEs: Adverse Events; d: day; ECG: electrocardiogram; ECOG: Eastern Cooperative Oncology Group; IERC: Independent Endpoint Review Committee; m: month; PBMC: peripheral blood mononuclear cell; PGx: pharmacogenomics; PK: pharmacokinetics; w: week.

Note: Where applicable, assessments performed prior to treatment unless otherwise indicated.

 All subjects who discontinue treatment will have at least one Follow-up Visit at 3 months (± 7 days) after last dose of study drug. Subjects who discontinue due to disease progression and/or start of a new line of therapy will then end participation in the trial. Subjects who received the maximum administrations of the combination of AGEN2034; who have achieved a complete response (CR) according to RECIST 1.1; or who have discontinued treatment due to reasons other than disease progression and/or start of a new line of therapy will be in Follow-up for up to approximately 12 months after last dose of study drug or until disease progression and/or start of a new line of therapy. Every effort should be made to collect subject information on the start of new antineoplastic therapy, disease progression and death.

 After the first Follow-up Visit, subjects that present(ed) with progressive disease and/or start new line of therapy will move into Survival Follow-up and should be contacted by telephone every 2 months for up to 12 months after last dose of study drug to assess for survival status. Post-study treatments and the subject's response to them will also be collected.

 Treatment administration and associated procedures for that visit may be delayed for treatment related AEs beyond the window and subsequent schedule adjusted accordingly.

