#### **6.3.4.2. Survival Follow-up (Phase 2 only)**

There is no survival follow-up for Phase 1.

For subjects in Phase 2, after the first Treatment Follow-up Visit, subjects with progressive disease and/or who start new line of therapy will move into Survival Follow-up. Subjects should be contacted by telephone to assess for survival status every 2 months for up to 12 months after their last dose of study drug.

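### Table 13 footnote 1 ends trial participation for the same Phase 2 subjects whom footnote 2 moves into survival follow-up, so OS may be censored informatively at sites that follow footnote 1

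*Protocol*

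**What the plan says.** Table 13 is the Phase 2 schedule. Its footnote 1 first guarantees one post-treatment contact: "All subjects who discontinue treatment will have at least one Follow-up Visit at 3 months". It then states: "Subjects who discontinue due to disease progression and/or start of a new line of therapy will then end participation in the trial". It closes with a general request that sets no timetable: "Every effort should be made to collect subject information on the start of new antineoplastic therapy, disease progression and death".

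Footnote 2, directly below, starts from the same first Follow-up Visit and says that "subjects that present(ed) with progressive disease and/or start new line of therapy will move into Survival Follow-up", with telephone contact every 2 months for at most 12 months from the last dose. Protocol 6.3.4.2 agrees: "subjects with progressive disease and/or who start new line of therapy will move into Survival Follow-up". So do the synopsis, 6.3.4.1, 6.4.1.9.1 and 6.4.1.9.2. Section 3.6 says that subjects withdrawn from treatment are followed for survival, and Table 13 has a Survival status row.

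OS time, median OS and OS rate are Phase 2 secondary endpoints (protocol 2.1.2, SAP 3.5). SAP 7.7.10 censors subjects who have not died at their last contact date.

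A second, smaller conflict concerns prohibited treatments. Protocol 5.5.2 says that subjects who, in the investigator's assessment, "require the use of any of the aforementioned treatments for clinical management should be removed from the trial". Section 4.4.1 refers to non-permitted drugs as defined in 5.5.2 "in which the predefined consequence is withdrawal from study drug", and adds that the sponsor may be consulted on whether treatment has to stop. Section 4.4.2, on leaving the trial, lists withdrawal of consent and joining another therapeutic trial. It does not list need for a prohibited treatment.

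**The concern.** A site cannot both end a subject's participation at the 3-month visit and call that subject every 2 months afterwards. If it acts on footnote 1, scheduled contact stops for subjects who have just progressed or changed therapy, and their risk of death is likely to be higher than that of subjects still free of progression. Under SAP 7.7.10 they are censored at that contact. Censoring then depends on prognosis, and the Kaplan-Meier curve, which treats censored subjects as having the same future risk as those still followed, tends to lie too high.

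The trial has a single arm, and protocol 8.1.2 allows historical data to be used in interpreting the endpoints. No concurrent arm with the same censoring would offset such a bias. With about 60 Phase 2 centers, different sites may well read the table differently.

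**Working it through.** **Plan figures.** The documents give no expected OS, OS event count or OS power, so there is no survival figure to reproduce. The stated design figures for efficacy concern ORR, and they reproduce. With 150 subjects the lower 95% Wilson limit exceeds 5% from 13 responses upward, and the exact power is 92.19% at a true ORR of 12% and 96.16% at 13%, against the stated 92.2% and 96.2%. These do not depend on survival contact.

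**Side by side, for a Phase 2 subject who stops for progression or new therapy**

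| Source | After the 3-month visit |
|---|---|
| Table 13 footnote 1 | Participation ends; unscheduled effort to learn of death |
| Table 13 footnote 2 | "will move into Survival Follow-up and should be contacted by telephone every 2 months for up to 12 months" |
| Synopsis, 6.3.4.1, 6.3.4.2, 6.4.1.9.1, 6.4.1.9.2 | Survival Follow-up |
| Table 13, Survival status row | Survival status recorded |

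Footnote 1 is the outlier. The same sentence is in the footnotes to Tables 11 and 12, and 6.3.4.2 says Phase 1 has no survival follow-up, so it fits there. The Phase 2 footnote also still speaks of a combination, although AGEN2034 is given alone. Both points suggest text carried over from elsewhere.

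**Deaths missed if footnote 1 alone is followed.** Inputs from the documents: last guaranteed contact at 3 months after last dose (footnote 1) and survival calls up to 12 months after last dose (footnote 2, 6.3.4.2). Assumptions not in the documents: exponential survival from last dose with median m months, m from 2 to 12, and no death found after month 3.

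With S(t) = 2^(-t/m), the share of deaths in months 0-12 that fall after month 3 is [S(3) - S(12)] / [1 - S(12)].

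| m (months) | S(3) | S(12) | Share missed |
|---|---|---|---|
| 2 | 0.354 | 0.016 | 34% |
| 3 | 0.500 | 0.062 | 47% |
| 4 | 0.595 | 0.125 | 54% |
| 6 | 0.707 | 0.250 | 61% |
| 8 | 0.771 | 0.354 | 65% |
| 12 | 0.841 | 0.500 | 68% |

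For m = 6: (0.707 - 0.250) / (1 - 0.250) = 0.457 / 0.750 = 61%. The share passes one half only when m exceeds about 3.4 months.

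**Trial-wide, worst case.** Suppose every site followed footnote 1 and affected subjects accounted for 60% to 90% of deaths (also an assumption). For m from 3 to 10 the loss would run from 0.60 x 0.467 = 28% to 0.90 x 0.668 = 60% of deaths within 12 months of last dose.

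These are shares of deaths missed. They are not the bias in median OS, which also depends on how far risk differs between subjects who have progressed and those who have not, and on how many sites follow footnote 1. Neither is known.

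**The case against.** The strongest reply is that nearly all of the protocol points the other way. The synopsis, Section 3.6, four subsections of Section 6, footnote 2 and a row of the table itself call for survival follow-up in Phase 2, so a careful site would follow them. Footnote 1 also asks for every effort to learn of deaths, so even a site reading it alone is not told to ignore them. OS is a secondary, single-arm estimate, and SAP 7.1 plans no formal hypothesis testing. All of this stands. It makes the loss smaller than the calculation if sites resolve the conflict sensibly, but it leaves a wrong instruction in the schedule, and an effort without a timetable does not replace scheduled calls.

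A reader might infer that OS will lose most of its deaths. The documents do not support that. They give no survival times, the share missed falls below one half for short medians, and a trial-wide loss needs many sites to disregard footnote 2. Nor does an assumed ORR of 12% to 13% show how many subjects stop for progression, since non-responders may have stable disease, stop for toxicity or die.

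A reader might also take 5.5.2 to expel subjects who progress and to end all contact with them. It does neither. It does not name progression, its list covers the Screening and Treatment periods, it prohibits nothing in post-treatment follow-up, and it is silent on later contact. Section 4.4.1 itself places the start of chemotherapy or new antineoplastic therapy under withdrawal from treatment.

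Nor does it follow that removal under 5.5.2 cuts off a full 90 days of AESI collection. Under 7.1.8 the window closes 30 days after a new anticancer therapy begins, if that is earlier.

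**Conclusion.** The contradiction between footnotes 1 and 2 is real and concerns the same subjects at the same visit. Footnote 1 is wrong for Phase 2 as written. A site that obeys it would censor OS informatively, and the Kaplan-Meier estimate would tend to be too high. The extent is unknown. At such a site, 34% to 68% of affected subjects' deaths within 12 months of last dose would be missed, given exponential survival after last dose, an assumed median of 2 to 12 months and no later death found. The primary endpoint, ORR, is not affected.

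The wording of 5.5.2 is a secondary inconsistency with 4.4.1 and 4.4.2. It should be reconciled, but it does not by itself show that subjects are lost to survival follow-up.

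**What to change.** In Table 13 footnote 1, replace the clause that ends participation with a statement that these subjects then enter Survival Follow-up as described in footnote 2. Tables 11 and 12 can stay as they are. Tell the Phase 2 sites, and ask them to recover vital status, where consent allows, for subjects already exited under footnote 1.

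Reconcile 5.5.2 with 4.4.1 and 4.4.2 so that removal for a prohibited treatment does not end survival follow-up. Whether study drug stops in that situation is a clinical matter for the protocol team and is not decided here.

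The cost is a small protocol amendment, with ethics approval where required (10.1), a site communication and some work to trace vital status. The telephone contacts are already part of the plan, so no new procedure is added. The sample size and the ORR analysis do not change.

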Subjects receiving AGEN2034 should be monitored for infusion reactions. This includes the measurement of vital signs for at least 1 hour after infusion. Subjects will remain in the clinic under close supervision for the duration of this monitoring period. Subjects with mild or moderate infusion reactions may receive AGEN2034 with close monitoring. Premedication with an antipyretic or antihistamine for subsequent treatment administration may be considered. For severe infusion reactions, AGEN2034 infusion must be discontinued, and appropriate medical therapy should be administered.

Subjects who do not experience any infusion related toxicity Grade 1 or higher during or after the infusion may be released from monitoring after one hour if they are otherwise stable.

Subjects with any infusion related toxicity must be managed as per the guidelines in [Table 3](#) and monitoring will continue until any infusion related toxicity has abated to less than Grade 1 and at least one hour has passed from the completion of the entire infusion and flush. All subjects will be given information on and instructions regarding both infusion related toxicity, which is expected to be most likely in the hour after completion of the infusion, and immune related AEs, before leaving the study site. This will include instructions on when and how to return for immune mediated toxicities associated with PD-1 blockade.

Once the AGEN2034 infusion rate has been decreased by 50% or interrupted due to an infusion-related reaction, it must remain decreased for all subsequent infusions. If the subject has a second infusion-related reaction that is Grade  $\geq 2$  on the slower infusion rate, infusion should be stopped and the subject should discontinue treatment. If a subject experiences a Grade 3 or Grade 4 infusion-related reaction at any time, the subject must discontinue treatment. If an infusion reaction occurs, all details about drug preparation and infusion must be recorded.

Should infusion reaction be considered a significant safety issue by the SMC, the SMC might decide to recommend premedication with an antihistamine and acetaminophen approximately 30 to 60 minutes before each dose of AGEN2034 (e.g., 25-50 mg diphenhydramine, 500-650 mg paracetamol IV or oral equivalent acetaminophen). This regimen may be modified based on local treatment standards and guidelines, as appropriate.

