 Core serum chemistry: alkaline phosphatase, alanine aminotransferase (ALT), aspartate aminotransferase (AST), blood urea nitrogen (BUN)/total urea, calcium, chloride, creatinine, glucose, magnesium, phosphorus/phosphates, potassium, sodium, total bilirubin. Results must be available prior to dosing.

 Full serum chemistry: core serum chemistry and albumin, amylase, cholesterol, creatine kinase, C-reactive protein (CRP), gamma glutamyl transferase (GGT), lactate dehydrogenase (LDH), lipase, total protein, triglycerides, uric acid. Results must be available prior to dosing.

 Hematology tests: absolute eosinophil count, absolute lymphocyte count, absolute neutrophil count (ANC), hematocrit, hemoglobin, mean corpuscular hemoglobin (MCH), mean corpuscular hemoglobin concentration (MCHC), mean corpuscular volume (MCV), platelet count, red blood cell (RBC), white blood cell (WBC) and differential count. Results must be available prior to dosing.

 Coagulation tests: activated partial thromboplastin time (aPTT), prothrombin time - international normalized ratio (INR). Results must be available prior to dosing.

 Endocrine function tests: adrenocorticotrophic hormone (ACTH), follicle-stimulating hormone (FSH) (if applicable), free thyroxine (T4), thyroid-stimulating hormone (TSH). Results must be available prior to dosing.

 Autoimmunity tests: anti-nuclear antibody, rheumatoid factor.

 Urinalysis including blood, glucose, protein, specific gravity, and microscopic exam if abnormal. Results must be available prior to dosing.

 Serum  $\beta$ -human chorionic gonadotropin ( $\beta$ -HCG) pregnancy test for women of child bearing potential at screening within 72 hours of first treatment dose (if performed earlier in screening period then a urine pregnancy test may be performed prior to first dose); urine pregnancy test at all other indicated visits (centers where urine pregnancy testing is not routine may substitute with serum  $\beta$ -HCG pregnancy test). Results must be available prior to dosing.

 AGEN2034 should be administered over 60 minutes (-10/+20 min). Subjects must be observed for 2 hours post-infusion for infusion-related reaction. If administration of AGEN2034 is delayed due to an AE, treatment visits may be delayed beyond the window of 3 days and schedules for subsequent visits should be adjusted accordingly.

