 Tumor tissue for biomarker analysis from a biopsy of a tumor lesion not previously irradiated must be available for PD-L1 expression and HPV evaluation. Only biopsies obtained at the time of or after the diagnosis of metastatic disease will be evaluated for PD-L1 expression. If a tumor biopsy was obtained from a target lesion during eligibility assessment, it is preferred to obtain a new baseline scan. Biopsy of lesions on study should be limited to non-target lesions or new lesions if their pathologic etiology is ambiguous. FOR SUBSEQUENT EVEN CYCLES: An **optional biopsy** is desired at Cycle 4 ONLY and, if provided, should be collected on Day 1 **before** AGEN2034 administration.

 Adverse events will be documented from time of consent up until 90 days after the last dose of study drug or the start of a new anticancer treatment, whichever comes first.

Following the End-of-Treatment Safety Follow-up Visit, only treatment-related AEs will be documented through the Treatment Follow-up Period of up to 12 months after the last dose of study drug or until disease progression and/or initiation of a new line of therapy.

 12-lead ECG on Cycle 1 Day 1, before AGEN2034 infusion starts and 2 hours (-10/+ 20 min) after infusion ends; on subsequent cycles as indicated 1 hour (-10 / + 20 min) after infusion ends or at visits indicated.

6a (At selected sites only) Expanded ECG Evaluation (triplicate tracings; see [Section 6.4.3.4](#)): 12-lead ECGs will be taken for Cycles 1 and 4 on Day 1 within 15 min ( $\pm$  10 min) before the Predose PK sample and within 15 min ( $\pm$  10 min) before the 30-min-after-end-of-infusion PK sample, and on Day 2 within 15 min ( $\pm$  10 min) before the 24-h-after-end-of-infusion PK sample. ECGs (12-lead, triplicate tracings) will also be taken for every subsequent 8th cycle for up to 1 year (approximately every 4 mo [in Cycles 12, 20, and 28]) on Day 1 within 15 min ( $\pm$  10 min) before the Predose PK sample and within 15 min ( $\pm$  10 min) before the 30-min-after-end-of-infusion PK sample.

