 Hematology Tests: absolute eosinophil count, absolute lymphocyte count, absolute neutrophil count (ANC), hematocrit, hemoglobin, mean corpuscular hemoglobin (MCH), mean corpuscular hemoglobin concentration (MCHC), mean corpuscular volume (MCV), platelet count, red blood cell (RBC), white blood cell (WBC) and differential count. Results must be available prior to dosing.

 Coagulation Tests: activated partial thromboplastin time (aPTT), prothrombin time - international normalized ratio (INR). Results must be available prior to dosing.

 Endocrine function tests: adrenocorticotropic hormone (ACTH), follicle-stimulating hormone (FSH) (for postmenopausal women if applicable), free thyroxine (T4), thyroid-stimulating hormone (TSH). Results must be available prior to dosing.

 Removed.

 Urinalysis including blood, glucose, protein, specific gravity, and microscopic exam if abnormal. Results must be available prior to dosing.

 Serum  $\beta$ -human chorionic gonadotropin ( $\beta$ -HCG) pregnancy test for women of child bearing potential at screening within 72 hours of first treatment dose (if performed earlier in screening period then a urine pregnancy test may be performed prior to first dose); urine pregnancy test at all other indicated visits. Results must be available prior to dosing.

 AGEN2034 should be administered over 60 min (-10/+20 min). For the first 2 cycles, subjects must be observed for 2 hours post-infusion for infusion-related reaction; for subsequent cycles subjects must be observed for at least 1 hour post-infusion for infusion-related reaction. If administration of AGEN2034 is delayed due to an AE, treatment visits may be delayed beyond the window of 3 days and schedules for subsequent visits should be adjusted accordingly.

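### Section 5.4.3 allows release one hour after any infusion, but the schedule footnotes require two hours' observation in Phase 1 and in Phase 2 Cycles 1 and 2

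*Protocol*

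**What the plan says.** Section 5.4.3 of the protocol (Treatment of Infusion Related Reactions) describes monitoring after each infusion. On the minimum period it says "This includes the measurement of vital signs for at least 1 hour after infusion", and it adds "Subjects will remain in the clinic under close supervision for the duration of this monitoring period". It then gives two release rules:

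- Subjects with no infusion-related toxicity of Grade 1 or higher "may be released from monitoring after one hour if they are otherwise stable".
- Subjects with such toxicity stay until it has fallen below Grade 1 and "at least one hour has passed from the completion of the entire infusion and flush".

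Neither rule is limited to a phase or a cycle.

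The schedules of assessments say something else. Footnote 20 of Table 11 (Phase 1 Part A1) reads "Subjects must be observed for 2 hours post-infusion for infusion-related reaction", and footnote 20 of Table 12 (Part A2) says the same. Neither limits the rule to particular cycles. Footnote 23 of Table 13 (Phase 2) reads "For the first 2 cycles, subjects must be observed for 2 hours post-infusion for infusion-related reaction", and then drops to a minimum of one hour for later cycles.

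**The concern.** A minimum of one hour, read alone, could coexist with a two-hour rule. Express permission to release at one hour cannot. Because Section 5.4.3 keeps subjects in the clinic only for the monitoring period, release from monitoring means the subject may go home.

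What is at stake is on-site management of a reaction in the second hour after an early infusion. Infusion-related reactions are the first risk listed in Section 2.2 and are adverse events of special interest at any grade under Section 7.1.8. The sponsor made the longer observation mandatory for early Phase 2 cycles, and the section that staff would open for infusion-reaction management removes it. About 60 Phase 2 centers could apply different rules. SAP Section 6.2 treats any departure from protocol procedures as a deviation, so a site could follow one section and be in deviation under another.

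**Working it through.** No sample size, power or event count is involved. The check compares the texts and then asks which other procedures keep a subject on site.

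**Step 1: the two rules side by side**

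| Setting | Section 5.4.3, earliest release | Schedule footnote | Agree? |
|---|---|---|---|
| Phase 1, all cycles | 1 hour | 2 hours (Tables 11 and 12, footnote 20) | No |
| Phase 2, Cycles 1 and 2 | 1 hour | 2 hours (Table 13, footnote 23) | No |
| Phase 2, Cycle 3 onward | 1 hour | at least 1 hour (Table 13, footnote 23) | Yes |

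Section 5.4.3 matches only the last row. The shortfall in the other rows is 120 − 60 = 60 minutes if nothing else holds the subject.

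**Step 2: is there a precedence rule?** Section 5.4.3 cross-refers to Table 3, which sets no release time for a reaction-free subject. Section 6.3.2 sends sites to the schedules for treatment-phase visit requirements, but it does not say that the schedules override Section 5.4.3. Section 6.4 sets no post-infusion observation time.

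**Step 3: Phase 2 Cycle 1.** Footnote 6 of Table 13 calls for "12-lead ECG on Cycle 1 Day 1, before AGEN2034 infusion starts and 2 hours (-10/+ 20 min) after infusion ends".

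- The window opens at 120 − 10 = 110 minutes and closes at 120 + 20 = 140 minutes.
- A subject who has this ECG is therefore on site for at least 110 minutes.
- The shortfall against two hours is at most 120 − 110 = 10 minutes.

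**Step 4: Phase 2 Cycle 2.** The same footnote puts later post-infusion ECGs "on subsequent cycles as indicated 1 hour (-10 / + 20 min) after infusion ends".

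- That window runs from 60 − 10 = 50 to 60 + 20 = 80 minutes, so an ECG here does not hold the subject for two hours.
- Table 14 has only predose blood samples at Cycle 2.
- The expanded ECG evaluation is scheduled at Cycles 1, 4, 12, 20 and 28, so it does not apply at Cycle 2.
- The full 60-minute shortfall is possible.
- Exposure: about 150 planned subjects × 1 infusion = about 150 infusions at most. Subjects who stop before Cycle 2, and sites that follow footnote 23, reduce this.

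**Step 5: Phase 1.** Footnote 7 of Tables 11 and 12 requires PK samples 2 and 4 hours after administration in Cycles 1 and 2, so subjects have procedures at and beyond two hours in those cycles. Where a later Phase 1 cycle includes a post-infusion ECG, it too is due at two hours (footnote 4). The exposed infusions are therefore later-cycle ones without such an ECG. Section 1 says Phase 1 enrollment was complete and some subjects were still participating. The number of remaining infusions is not given.

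**The case against.** The strongest reply is that the texts differ but do not collide. Section 5.4.3 grants a permission, the footnotes impose a duty, and a site that holds everyone for two hours satisfies both. Section 6.3.2 points sites to the schedules. Section 5.4.3 itself expects infusion toxicity mainly in the first hour after the infusion, gives all subjects instructions before they leave, and keeps anyone with a reaction until it has abated. Early Phase 1 cycles are covered by the PK samples. The SAP describes fast accrual late in enrollment and a filing analysis of all dosed subjects with at least 12 months' median follow-up. This suggests, without stating it, that few Phase 2 Cycle 2 infusions were left by then. An amendment also needs submission under Section 10.1 and roll-out to about 60 centers.

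Most of this is correct, and it limits the size of the problem. It does not reconcile the texts. Nothing tells a site to follow the stricter one, and the Section 6.3.2 pointer is not a precedence clause. If the first hour carries most of the risk, the benefit of the second hour is smaller, but the sponsor still made it mandatory. The point about cost is fair: the wording change is small, but an amendment has administrative steps.

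**Conclusion.** The concern holds. The protocol is wrong as written: Section 5.4.3 permits release at one hour where the schedules require two, in all Phase 1 cycles and in Phase 2 Cycles 1 and 2.

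The consequence is modest. In Phase 2 it falls mainly at Cycle 2, with up to 60 minutes less observation at no more than about 150 infusions. That upper bound assumes all planned subjects reach Cycle 2 and every site uses the one-hour permission. At Phase 2 Cycle 1 the loss is at most about 10 minutes, assuming the ECG is done within its window. For Phase 1 the remaining exposure cannot be counted from the documents. They give no rate of second-hour reactions, so the clinical harm cannot be quantified.

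There is no effect on the ORR analysis. There is no material effect on capture of adverse events of special interest, because adverse events are reviewed at later visits and every infusion reaction is reportable whatever its grade. This should be corrected as a safety instruction. It does not threaten the trial's conclusions.

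**What to change.** Reword the monitoring and release sentences in Section 5.4.3 so that they carry the same times as the footnotes. For example:

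> The minimum observation period after infusion is 2 hours in Phase 1 (all cycles) and in Phase 2 Cycles 1 and 2, and 1 hour from Phase 2 Cycle 3 onward. A stable subject without infusion-related toxicity may leave when this period ends. A subject with infusion-related toxicity stays until it is below Grade 1 and the period has ended.

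The footnotes need no change. If the sponsor prefers not to state the times twice, Section 5.4.3 could instead refer to the footnotes for the minimum period and drop its own one-hour figures.

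The cost is wording in one section, plus the usual submission and site notification, which can go with the next amendment. No new procedure, visit or data item is needed, because the two-hour rule is already in the schedules.
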